Sample Size calculations: The estimated sample size needed to have sufficient power to detect a moderate effect size (using a Cohen's d of 0.3 as the reference) is 240 children, or 120 per arm. Based on our preliminary data, for each academic year, the average BMI change ranges from 0.35 to 0.55 units, with a standard deviation that varies across ethnic groups and years from 0.80

to 1.00. An example of an effect between two groups or time points that would match a Cohen's d of 0.3 would be one group in which the children on average increases their BMI by 0.5 units, and another group where participants increase their BMI by 0.2 units (0.3 unit difference), with standard deviations of 1.0. These effects (BMI difference of 0.3kgm^2) are just above the mean weighted effect size reported in the most comprehensive and recent meta-analysis on childhood obesity studies of 0.30kg/m^2 .^{9,10} With a two-tailed test and alpha level of 0.05, a sample size of 80 children per arm (a retention rate of 67%) would result in an associated statistical power $\geq 80\%$ to detect intervention effects between arms from one time point to the next. With very similar parameters and sample sizes, prior research has indicated that based on simulation studies,¹⁷ these parameters demonstrated excellent power ($\geq 80\%$) in detecting these size differences.

Institutional Review Board:

All protocol activities were approved by the Institutional Review Board of Northern Arizona University (protocol #1193689) and the Flagstaff Unified School District. Parental consent forms and children assent were attained for each participant.

References:

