COVER PAGE

Study Title: Addressing Health Disparities in Childhood Obesity, One Summer at a Time

Clinical Trials Registration Number: NCT03595332

Date of document: July 14, 2022

Statistical Analysis Plan

The proposed statistical analyses for the current study includes a nested regression model utilizing Generalized Estimating Equations with an exchangeable working correlation matrix to account for the nested data structure of children within schools and families. For all variables, 95% Confidence intervals will be reported (for b in models with a linear response variable and Odds Ratios for models with an ordinal logistic response variable) and a significance level of $p=0.05$ will be used to test hypotheses.

For the primary analysis, we propose to test the difference in Body Mass Index (BMI) Percentile-scores for age and sex based on Centers for Disease Control and Prevention (CDC) criteria from Baseline to 10-weeks using GEE models with a linear response variable. We will test whether the difference is significantly different from zero, adjusting for age (included as a covariate) and sex and ethnicity (included as factors). We will also test whether the immediate intervention group was significantly different from the delayed intervention group by including a variable denoting immediate vs delayed group membership. We will test the null hypothesis that participants in the intervention did not significantly change their BMI Percentile-score.

For the second primary analysis, we will test whether the BMI Percentile from baseline to 10-weeks was significantly different from zero among the highest-risk children, defined as those participants with a baseline BMI Percentile score equal to or greater than the 85th percentile as considered by the Centers for Disease Control and Prevention. GEE models will be used restricting the sample to children with overweight at baseline.

For the first secondary analysis, we propose to test the difference in Body Mass Index Percentile-score from Baseline to 1-year follow-up using GEE models with a linear response variable. We will test whether the difference is significantly different from zero, adjusting for age (included as a covariate) and sex and ethnicity (included as factors). We will test the null hypothesis that participants in the intervention did not significantly change their BMI Percentile-score.

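### The protocol's claim of at least 80% between-arm power with 80 children per arm is wrong on its own inputs: power is about 47%, and about 64% with all 120 per arm

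*Protocol*

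**What the plan says.** The Sample Size calculations section of the protocol opens with "The estimated sample size needed to have sufficient power to detect a moderate effect size", "using a Cohen's d of 0.3 as the reference", and gives that size as 240 children, 120 per arm. The worked example is a mean BMI change of 0.5 units in one group and 0.2 in the other, with SD 1.0. Preliminary data on BMI change over an academic year are described "with a standard deviation that varies across ethnic groups and years from 0.80" to 1.00.

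For a two-tailed test at alpha 0.05 the section then says that "a sample size of 80 children per arm (a retention rate of 67%) would result in an associated statistical power" of at least 80% "to detect intervention effects between arms from one time point to the next". It adds that simulation work cited from another trial, with similar parameters, also showed at least 80%. It states no correlation, covariate R-squared, intraclass correlation or design effect.

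The SAP gives no power calculation. Its primary analysis uses GEE "to account for the nested data structure of children within schools and families" and contains two tests. One concerns change from baseline: "We will test the null hypothesis that participants in the intervention did not significantly change their BMI Percentile-score". The other compares the groups: "We will also test whether the immediate intervention group was significantly different from the delayed intervention group".

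**The concern.** Every input for a two-sample power calculation is stated: effect, SD, alpha, sidedness, number per arm and contrast. The claim can therefore be checked directly. A between-arm d of 0.3 is a small-to-moderate effect, and 80 per arm is well short of what it usually takes to detect one.

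The immediate-versus-delayed test is the only planned comparison with a concurrent group. If its power is believed to be at least 80%, a non-significant result will be taken as fair evidence that an effect of the planned size is absent. If the power is nearer one half, that reading is not justified.

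**Working it through.** **Inputs** (all from the protocol's Sample Size calculations section)
- Difference in mean BMI change: 0.5 − 0.2 = 0.3 units
- SD of change: 1.0 in the example, so d = 0.3; range 0.80 to 1.00
- Two-tailed alpha: 0.05
- Enrolled: 120 per arm. Analysed: 80 per arm. Retention: 80/120 = 66.7%, which matches the stated 67%
- Contrast: between arms
- Independence of observations: assumed here, because no clustering figure is given

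**1. The plan's figure.** For two groups of n, the t statistic has noncentrality d × √(n/2) on 2n − 2 degrees of freedom. At n = 80 the noncentrality is 0.3 × √40 = 1.897 and the two-sided critical value is 1.975. The expected statistic falls below the critical value, so power must be under one half. The noncentral t gives **47.1%**. The stated figure of at least 80% is not reproduced; the gap is about 33 percentage points.

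**2. Other SDs and no attrition** (two-sided, 0.3-unit difference)

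| SD | d | 80 per arm | 120 per arm |
|---|---|---|---|
| 1.0 | 0.300 | 47.1% | 63.9% |
| 0.9 | 0.333 | 55.4% | 73.0% |
| 0.8 | 0.375 | 65.4% | 82.5% |

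A simulation of 50,000 trials with means 0.5 and 0.2 and SD 1.0 agrees: 47.5% at 80 per arm and 64.1% at 120. The only cell above 80% needs both the smallest SD and no loss to follow-up.

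**3. Number needed.** The normal approximation is n = 2(1.960 + 0.842)²/0.3², about 175 per arm. With the t distribution it is **176 analysed per arm**, more than twice 80.

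**4. Detectable effect at 80% power.** d = 0.446 at 80 per arm and 0.363 at 120 per arm. On the protocol's BMI scale, 80 per arm corresponds to 0.446 units at SD 1.0, or 0.446 × 0.8 = 0.357 units at SD 0.8.

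**5. What would rescue the claim at 80 per arm.** The SD would have to be 0.3/0.446 = 0.673, below the stated range. Equivalently, at SD 1.0, covariates would have to explain 1 − 0.673² = 0.547 of the variance of change. The SD already describes change, so the gain from pairing is already counted. A one-sided test, contrary to the text, gives only 59.7% at SD 1.0 and 76.3% at SD 0.8.

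**6. Precision.** The 95% CI half-width is t(0.975, 2n − 2) × √(2/n): 1.975 × √(2/80) = 0.312 SD at 80 per arm, and 0.254 SD at 120 per arm. With 80 per arm, an estimate of exactly zero therefore still leaves d = 0.3 inside the interval.

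**7. The other contrast.** A one-sample test of change at d = 0.3 has power 75.5% with n = 80 and 96.5% with n = 160. This is not the contrast the protocol names.

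**The case against.** The best case for the plan has five parts.

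- **The named null is change against zero.** The SAP's stated null is no change within participants, and the group comparison is added to it. One-sample power is much better: at n = 80 and a 0.3-unit change it is 84% at SD 0.9 and 91% at SD 0.8. The protocol's example also speaks of two groups or time points, so a one-sample contrast may have been in mind. This limits the consequence to how the between-arm result is read. It does not rescue the claim, because the power sentence itself says between arms.
- **The cited simulations.** They cannot be examined here. However, the protocol quotes no parameter from them that would supply the roughly 55% explained variance required, and the power sentence is offered on its own inputs.
- **Confidence intervals are already promised.** The SAP reports 95% intervals for all variables. That helps, but it does not correct the stated power or say how a null result will be interpreted.
- **The zero-estimate argument depends on the SD.** In SD units against d = 0.3 it is correct at 80 per arm. Against a fixed 0.3 BMI units the half-width is 0.312 at SD 1.0, 0.281 at SD 0.9 and 0.250 at SD 0.8, so below an SD of about 0.96 (0.3/0.312) a zero estimate would exclude 0.3 units. At 120 per arm, 0.3 SD is excluded as well. This qualification stands. Non-zero, non-significant estimates can still be compatible with the target.
- **The scale differs.** The protocol's SDs are for raw BMI over an academic year, while the SAP analyses BMI percentile over 10 weeks. Detectable effects in kg/m² should be labelled accordingly.

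**Conclusion.** The power statement is wrong as written and should be corrected. For the stated contrast and inputs, power is about 47% with 80 per arm, not at least 80%, and about 64% with 120 per arm. Nor does 120 per arm reach 80% at d = 0.3 with full retention; it passes 80% only at the lowest SD, where d is 0.375.

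These figures assume independent observations, equal arms and no variance reduction beyond the use of change scores. Clustering by school and family is left out, and its direction depends on the unit of allocation, which the documents do not state. As an illustration only, if arms were allocated by cluster with an assumed 40 analysed children per cluster, power at 80 per arm (normal approximation) would be about 36% at an assumed intraclass correlation of 0.01 (design effect 1 + 39 × 0.01 = 1.39) and about 20% at 0.05 (design effect 2.95).

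The consequence is confined to the immediate-versus-delayed result. The test of change against zero is not affected by this error.

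**What to change.** Replace the power sentence in the protocol, or record the correction in the SAP, along these lines:

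> Assuming independent observations, 80 analysed children per arm give about 47% power for a between-arm d of 0.3 (about 64% with 120 per arm). Power of 80% is reached at a d of about 0.45 with 80 per arm, which on the academic-year BMI scale is 0.45 kg/m² at SD 1.0 or 0.36 kg/m² at SD 0.8. Clustering within schools and families is not included and may change these figures, depending on how arms are allocated.

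Add to the SAP's primary analysis:

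> A non-significant between-arm result does not by itself rule out d = 0.3 and will be interpreted from its 95% confidence interval.

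If a different contrast or a variance-reducing model was in fact powered, name it and give its correlation or R-squared so that the figure can be reproduced.

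The change takes a few sentences. Its only cost is a less favourable stated power; no further enrolment is asked for.

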COVER PAGE

Study Title: Addressing Health Disparities in Childhood Obesity, One Summer at a Time

Clinical Trials Registration Number: NCT03595332

Date of document: April 15, 2018

Study Protocol

Background

Childhood obesity is one of the most urgent health challenges of our time. Obesity rates of Native American and Hispanic children are far higher than national averages, placing these children at high risk for early mortality, cardiovascular and metabolic conditions including diabetes, depression and overall poor quality of life.¹⁻³ By the 5th grade, approximately 50% of Hispanic and Native children are already overweight, and Native children have type 2 diabetes rates 9 times higher than non-Hispanic Whites.⁴ In our area, obesity rates are highly concentrated: most obese and overweight children are enrolled in 4 of the 10 elementary schools, which include primarily underserved Hispanic and Native American children.

Recent research has further demonstrated that the 'obesity gap' facing minority students is largely due to summer weight gain.⁵⁻⁹ Based on local data, it was confirmed that children in our school district were much more likely to worsen their weight-related health status during the summer than during the schoolyear. However, statewide, only 22% of children participate in summer activities, despite 65% of parents expressing interest.¹⁰ Finally, ages 7 to 11 have been found in national data to see a sharp increase in obesity rates.¹¹ Indeed, locally in 2015, approximately 20% of 7 year-olds are overweight or obese, but 35% of 11-year olds. Thus, we know which populations are at highest risk, at what developmental age changes occur most rapidly (ages 7-11) and that interventions are most needed in the summer, but that this need is not being met.

A modest amount of research has evaluated summer programming, but almost none among Native Americans/Hispanics. In the early 2000s, the CDC developed a 'Summer Scorecard' intervention,¹² a partnership with local businesses to provide children with a 'scorecard' of subsidized or free local activities. The VSS has not been tested among Hispanic and Native American children. Therefore, this study assessed the effectiveness of the VSS among children ages 5-13 in the 4 highest risk schools in the Flagstaff area. Outcomes included body composition (BMI) percentile score, reported physical activity and self-efficacy using survey instruments previously developed and tested by the CDC.

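### The stated power of at least 80% makes no allowance for clustering in families and schools; correcting the two-sample arithmetic alone would still overstate it if siblings or whole schools are allocated together

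*Protocol*

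**What the plan says.** The protocol (Sample Size calculations) takes a standardised difference of 0.3 ("using a Cohen's d of 0.3 as the reference"), illustrated by a 0.3-unit difference in BMI change with a standard deviation of 1.0. The enrolment target "is 240 children, or 120 per arm". The test is two-sided at the 5% level. The power claim is that "a sample size of 80 children per arm (a retention rate of 67%) would result in an associated statistical power" of at least 80% for the comparison between arms. It adds that simulation studies in earlier research, with similar parameters, support this. No intraclass correlation, cluster size, number of clusters or design effect appears.

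The SAP (opening paragraph) chooses generalized estimating equations (GEE) with an exchangeable working correlation "to account for the nested data structure of children within schools and families". The protocol (Background) places the study "among children ages 5-13 in the 4 highest risk schools in the Flagstaff area". The SAP compares an immediate with a delayed intervention group. Neither document says whether children, families or schools were allocated to those groups, or how.

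**The concern.** The two documents treat the children differently. The SAP regards correlation within families and schools as important enough to determine the model. The sample-size section offers only an effect size, an alpha level and a count of children.

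This is separate from the fact that the two-sample calculation does not reach 80%. A sponsor who corrected only that calculation would get a new figure that still counts every child as independent. If siblings are kept in one group, or whole schools are assigned, and changes in BMI are positively correlated within those units, that figure would again be too high and the detectable difference too small. A null between-arm result could then be read as evidence against a 0.3-unit effect on the strength of power the trial did not have.

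**Working it through.** **Inputs from the protocol (Sample Size calculations, Background).** Two-sided alpha 0.05; d = 0.3; SD 1.0; 120 enrolled and 80 retained per arm (80/120 = 67%); 4 schools.

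**Assumptions, because the documents give none.** Families: average m of 1.2 to 2 enrolled children, correlation 0.2 to 0.5. Schools: two per arm, ICC 0.005 to 0.05. Normal (large-df) approximation throughout unless noted.

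**Step 1: the stated figure.** Power = Φ(d√(n/2) − 1.960).
- With n = 80: 0.3 × √40 = 1.897, and Φ(1.897 − 1.960) = 47.5% (exact noncentral t: 47.1%). The stated 80% is not reproduced.
- Nearby variants: one-sided, 60.0%; SD 0.8, the lower end of the protocol's range, 66.0%; 120 per arm with no loss, 64.2%. Only 120 per arm with no loss and SD 0.8 passes 80% in a two-sided two-arm test (82.8%), and that is not the scenario stated.
- Needed for 80%: n = 2(1.960 + 0.842)²/0.3² = 174.4, so 175 per arm (176 by exact t).

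**Step 2: clustering at the planned sizes.** Design effect DE = 1 + (m − 1) × ICC; effective n = n/DE; detectable d = 2.802 × √(2/effective n). The school rows use m = n/2, because there are two schools per arm.

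| Per arm | Allocation (assumed) | m | ICC | DE | Effective n per arm | Power | Detectable d |
|---|---|---|---|---|---|---|---|
| 80 | independent children | – | – | 1.00 | 80.0 | 47.5% | 0.44 |
| 80 | family | 1.2 | 0.2 | 1.04 | 76.9 | 46.0% | 0.45 |
| 80 | family | 2 | 0.5 | 1.50 | 53.3 | 34.1% | 0.54 |
| 80 | school | 40 | 0.005 | 1.195 | 66.9 | 41.1% | 0.48 |
| 80 | school | 40 | 0.05 | 2.95 | 27.1 | 19.6% | 0.76 |
| 120 | independent children | – | – | 1.00 | 120.0 | 64.2% | 0.36 |
| 120 | family | 1.2 to 2 | 0.2 to 0.5 | 1.04 to 1.50 | 115.4 to 80.0 | 62.5% to 47.5% | 0.37 to 0.44 |
| 120 | school | 60 | 0.005 to 0.05 | 1.295 to 3.95 | 92.7 to 30.4 | 53.3% to 21.5% | 0.41 to 0.72 |

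**Step 3: if only the two-sample arithmetic is corrected.** At 175 per arm, independent children give 80.1%.
- Family design effects of 1.04 to 1.5 reduce this to 78.6% to 63.0%.
- With two schools per arm, m = 87.5, DE is 1.43 to 5.33, and power is 65.0% to 22.8%.

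**Step 4: the ceiling set by 4 schools.** With two schools per arm, effective n = n/[1 + (n/2 − 1) × ICC], which approaches 2/ICC as n grows.
- At ICC 0.05 the limit is 40 per arm. Φ(0.3 × √20 − 1.960) = Φ(−0.618) = 26.8%, so power stays below about 27% at any enrolment.
- At ICC 0.005 the limit is 400. About 310 per arm would reach 80% (m = 155, DE = 1.77, effective n = 175.1).

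**Step 5: individual allocation.** If the arms are balanced within each cluster, the between-arm variance is multiplied by about (1 − ICC). At ICC 0.05 and 80 per arm, power is 49.5% against 47.5%. There is no loss.

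**The case against.** The strongest reply is that the further loss depends on facts the documents do not give. Every cluster size and correlation above is assumed, and individual allocation would remove the between-arm penalty. That stands. A reader might infer that the between-arm test is certain to lose power through clustering; the documents do not support that. They do show a power claim that cannot be verified without the unit of allocation.

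Second, the cited simulations may have modelled clustering. They may, but the protocol mentions only similar parameters and sample sizes. It does not say that clustering was included or that the design had 4 schools and siblings.

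Third, most of the gap from 80% to 47% belongs to the two-sample arithmetic, and assumed family clustering adds only about 1 to 13 points. This is correct, and one recalculation can deal with both.

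Fourth, it is tempting to conclude that the planned GEE analysis will report wider standard errors. That is not assured: with about 4 clusters, uncorrected sandwich standard errors tend to be too small. It is also tempting to refer a school comparison to t on 2 degrees of freedom. The SAP states no such test, and most of that loss would come from the degrees of freedom (about 20% power at 80 per arm even with a design effect of 1).

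Finally, the SAP's primary null hypothesis is change from zero in the pooled sample. Sibling correlation widens that standard error under any allocation, and school correlation does so if the 4 schools are treated as a sample of schools. They were chosen as the highest-risk ones, so that treatment is debatable. At the worst assumed family design effect, 160/1.5 = 107 effective children still give Φ(0.3 × √106.7 − 1.960) = 87% power for a change of 0.3 SD. The protocol's power claim concerns the between-arm contrast, so the pooled test neither carries this point nor answers it.

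**Conclusion.** The point holds in conditional form. The claim of at least 80% power at 80 per arm is not met for independent children (about 47%), and it carries no clustering allowance although the SAP models clustering. If families or schools are the unit of allocation and correlation in BMI change is positive, a corrected two-sample figure would still be too high. At 80 per arm the assumed ranges give about 46% to 34% for families and 41% to 20% for schools.

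A reader might also infer that enrolling more children would always restore power. With 4 schools allocated whole, that fails at the upper assumed ICC, where the ceiling is about 27%. The size of the loss cannot be fixed from the documents, because the allocation unit and the correlations are missing. The defect should be corrected, but the claim must not go beyond that condition.

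**What to change.** In Sample Size calculations:
- Name the unit allocated to immediate or delayed intervention.
- Apply 1 + (m − 1) × ICC for that unit, with m tied to the actual number of clusters. For schools, m grows with enrolment.
- Take the ICC from the preliminary district data where identifiers allow; otherwise show a range. The protocol's Measures section lists school membership but no family identifier, so a range may be all that is possible for families. Those data are academic-year BMI changes, whereas the SAP's endpoint is 10-week change in BMI percentile; say so when using them.
- Restate effective n, power and detectable difference for 80 and 120 per arm, in the same recalculation that corrects the two-sample figure.
- If the cited simulations did include clustering, state the cluster structure and correlations they used.

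The cost is one recalculation and a few sentences, with a less favourable stated power. No extra enrolment is asked for.

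### The plan allows for one third loss but states no missing-data method; the GEE as described appears to use only children with both measurements and leaves out baseline BMI percentile, school and survey scores as predictors of loss

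*Protocol*

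**What the plan says.** The protocol's sample size section sets enrolment: the number needed "is 240 children, or 120 per arm". It then bases the power statement on 80 children per arm, "a retention rate of 67"%, so it allows for losing one child in three.

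The SAP's primary analysis tests the difference in BMI percentile between baseline and 10 weeks "using GEE models with a linear response variable". Age is a covariate, sex and ethnicity are factors, and an immediate/delayed indicator is added to compare groups. The stated null hypothesis is that participants' BMI percentile did not change. The exchangeable working correlation covers children within schools and families; repeated visits within a child are not named. The second primary analysis restricts the sample to children at or above the 85th percentile at baseline, and the secondary analyses use GEE for 1-year BMI percentile and 10-week self-efficacy.

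Neither document mentions missing data, imputation, weighting, an analysis population, a comparison of lost with retained children, or a sensitivity analysis.

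**The concern.** Testing a difference against zero, with clustering only by school and family, reads as one change value per child. A child without a 10-week measurement then has no value and contributes nothing. With a third of each arm allowed to go missing, the result describes all enrolled children only if, within levels of the model's covariates, those lost would have changed as much as those retained.

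The model omits several measured variables that could predict both loss and change: baseline BMI percentile, school as a predictor (it enters only as a cluster), and the baseline survey scores. The SAP itself treats baseline weight status as important, since it gives the higher-risk children a primary analysis of their own.

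The test against zero is the more exposed of the two primary questions. It has no comparison arm to cancel a selection effect common to both groups, so completers who did better than the children lost could make a null result look like a change.

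**Working it through.** **Inputs from the protocol's sample size section.** 120 enrolled and 80 retained per arm; target difference 0.3 BMI units; standard deviation 1.0 in the worked example ("0.3 unit difference), with standard deviations of 1.0"); two-sided alpha 0.05. **Inputs assumed here.** The gap in mean change between lost and retained children, and all simulation coefficients. The BMI scale is used because the documents give no standard deviation for percentile change.

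**1. The plan's retention figure.** 80/120 = 66.7%, which reproduces the stated 67%. The lost fraction is f = 40/120 = 0.333. (The power of at least 80% claimed for 80 per arm does not reproduce: d = 0.3, two-sided 0.05 gives 47.5%. That is a separate matter, and nothing below depends on it.)

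**2. Shift in an arm mean.** Full mean = (1 − f) × retained mean + f × lost mean. So full mean − completer mean = f × (lost mean − retained mean).

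| Assumed gap (kg/m²) | Shift = 0.333 × gap | Share of 0.3 |
|---|---|---|
| 0.1 | 0.033 | 11% |
| 0.2 | 0.067 | 22% |
| 0.3 | 0.100 | 33% |

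If the gap exists in one arm only, the shift is also the bias in the between-arm contrast. If gap and loss rate are equal in both arms, the contrast is unbiased and the whole shift falls on the test against zero.

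**3. Effect on the test against zero.** Take all 160 retained children together, standard deviation 1.0, no clustering: SE = 1/√160 = 0.079. With no true change, the rejection probability is P(|Z + shift/SE| > 1.96). The ratios shift/SE are 0.42, 0.84 and 1.26, and the nominal 5% error rate becomes about 7%, 13% and 24%.

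**4. Which mechanisms matter.** A large simulation (2 million children, least-squares mean model on completers, about 67% retained) set true mean change at 0.35 and true arm difference at −0.30. Mean change is evaluated at the covariate means of all enrolled children.

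| Loss driven by | Mean change | Arm difference | After adding baseline BMI |
|---|---|---|---|
| Age, or arm and age (in model) | 0.35 | −0.30 | unchanged |
| Baseline BMI, both arms | 0.27 | −0.30 | 0.35; −0.30 |
| Baseline BMI, intervention arm only | 0.31 | −0.38 | 0.35; −0.30 |
| The change itself, both arms | 0.15 | −0.27 | 0.17; −0.28 |
| The change itself, intervention arm only | 0.25 | −0.50 | 0.26; −0.48 |

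Loss explained by covariates in the model does no harm. Loss explained by baseline BMI harms the test against zero, and also the contrast when it acts in one arm; adjustment repairs both. Loss driven by the change itself is not repaired by baseline adjustment, which is why a not-at-random analysis is needed.

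One proviso: where loss depended on age, the raw completer mean was 0.295, and 0.35 was recovered only at the enrolled children's covariate means. The SAP does not say at what covariate values its test against zero is made.

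**The case against.** Several objections are fair, and they limit the point.

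- A reader might infer that the model ignores every predictor of loss. It does not: age, sex, ethnicity and, in the between-group test, group are included, and loss that depends only on these causes no bias in the adjusted estimates.
- A reader might take 67% as a forecast or an observed result. It is a planning allowance in a power statement, not tied to the 10-week visit or to either arm.
- The SAP never states that it uses change scores or completers; that form is inferred. If baseline and follow-up were instead entered as repeated values, unweighted GEE would still generally need loss to be unrelated to outcome given the covariates, and the stated correlation structure does not represent repeated values within a child.
- It is tempting to conclude that less engaged families would be lost and that the result would favour the programme. The documents do not establish this. The protocol's Measures section has height and weight taken at school during the school day, so measurement is not described as depending on family attendance or on returning a scorecard. Moves and absence remain possible, but nothing links them to engagement or arm.
- The gaps are assumed and are on the BMI scale, while the outcome is BMI percentile.
- Engagement data may be missing for the same children who are lost, and nothing shows that those missing at 10 weeks have a 1-year value.

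What remains is that a plan built around losing up to a third of each arm has no method for it, and leaves out baseline variables that could reduce the risk.

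**Conclusion.** The concern holds as a material risk that the plan leaves untreated, not as a demonstrated bias. As described, the primary GEE appears to use only children with both measurements, and is valid only if loss is unrelated to BMI-percentile change given age, sex, ethnicity and, where fitted, group. Selective loss alike in both arms mainly damages the stated test of change against zero; selective loss that differs by arm also damages the immediate-versus-delayed contrast.

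At 33% loss and assumed gaps of 0.1 to 0.3 kg/m², an arm mean moves by 0.03 to 0.10 kg/m², or 11% to 33% of the 0.3-unit target. These sizes illustrate the issue on the BMI scale and cannot be converted to the percentile scale from the documents. Neither the direction nor the presence of bias can be read from the plan. The change should be made, since it uses planned measurements and the analysis as written does worse under plausible loss.

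**What to change.** 1. State the missing-data assumption, and compare lost with retained children by arm on baseline characteristics.
2. Add baseline BMI percentile to the model, and evaluate the test against zero at the covariate means of all enrolled children.
3. Run the GEE after multiple imputation by arm, or with inverse-probability weights. Use baseline BMI percentile, age, sex, ethnicity, school, baseline survey scores and the other follow-up BMI where observed (1-year for a missing 10-week value, and the reverse). The procedure should respect clustering by school and family.
4. Add a not-at-random sensitivity analysis that shifts imputed BMI by 0.1 to 0.3 kg/m² in each arm separately and in both arms together. Apply the shift before converting to percentiles, because a given BMI shift has no fixed percentile equivalent across age, sex and starting BMI.
5. Report the completer GEE alongside.

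The cost is some extra programming and slightly longer reporting, with no new data. The main downside is that imputation or weighting rests on a missing-at-random assumption of its own. The protocol describes study conduct in the past tense and the SAP is dated July 14, 2022; if outcomes have already been seen, the imputation analysis should be labelled supplementary.
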